Appendix G ECOG Scale for Performance Status

Grade	Description
0	Normal activity. Fully active, able to carry on all predisease performance without restriction.
1	Symptoms but ambulatory. Restricted in physically strenuous activity, but ambulatory and able to carry out work of a light or sedentary nature (eg, light housework, office work).
2	In bed <50% of the time. Ambulatory and capable of all self-care, but unable to carry out any work activities. Up and about more than 50% of waking hours.
3	In bed >50% of the time. Capable of only limited self-care, confined to bed or chair more than 50% of waking hours.
4	100% bedridden. Completely disabled. Cannot carry on any self-care. Totally confined to bed or chair.
5	Dead.

Source: Oken MM et al, 1982(Oken et al. 1982). ECOG: Eastern Cooperative Oncology Group.

Appendix H Operating Characteristics of the Futility Stopping Rules

The stopping rules used for the treatment arms of 240 mg and 120 mg at each interim futility analysis were chosen to have reasonable operating characteristics as displayed in this section (Appendix H Table 1 and Appendix H Table 2).

Based on the proposed 2 interim futility analyses criteria (Section 13.2.2.1 Part 3 Futility Stopping Rules), the design operating characteristics were calculated for each of the treatment arms under different true ORR scenarios.

Appendix H Table 1 displays the corresponding operating characteristics for the treatment arm of 240 mg, including cumulative probability of terminating the arm early at each interim analysis, average number of patients enrolled and followed up for 3 months, average number of responders observed, and probability of success (PoS) at primary analysis. As there is no plan for efficacy claim based on any of the interim analyses, the only time to claim a positive efficacy conclusion (success for each arm) will be at the primary analysis. The success criterion will be a minimal of 33 responders among 118 treated patients, achieving the goal of lower limit of 95% CI above 20% uninteresting rate.

Appendix H Table 1 Operating Characteristics for the Treatment Arm of 240 mg

	_	llity of terminating the early at	PoS at primary	Average number of patients	Average number of
True ORR	1st IA for Futility	2 nd IA for futility	analysis	enrolled and followed up for 3 months	observed responders
10%	82%	99%	0%	21	2
20%	40%	70%	2%	56	11
30%	13%	19%	64%	101	30
35%	6%	8%	89%	111	39
40%	3%	3%	97%	115	46
50%	<1%	<1%	100%	118	59

IA: interim analysis; ORR: objective response rate; PoS: probability of success.

As shown in Appendix H Table 1, when the true ORR is 20%, there is about 40% chance to terminate the 240 mg arm at the first interim futility analysis; about 70% chance to terminate the arm at either the first or second interim futility analysis; probability of success at primary analysis is around only 2%. When the true response rate is 35%, the cumulative probabilities of terminating the arm are reduced to 6% and 8% at the first and second interim futility analyses, the probability of success at primary analysis is 89%.

A similar operating characteristics table was created for the treatment arm of 120 mg (Appendix H Table 2).

Appendix H Table 2 Operating Characteristics for the Treatment Arm of 120 mg

True	Cumulative probability of terminating the arm early at		PoS at primary	Average number of patients enrolled and	Average number of observed
ORR	1st IA for Futility	2 nd IA for futility	analysis	followed up for 3 months	responders
10%	55%	99%	0%	30	3
20%	17%	66%	2%	67	13
30%	4%	13%	68%	108	32
35%	1%	4%	93%	115	40
40%	1%	1%	99%	117	47
50%	<1%	<1%	100%	118	59

IA: interim analysis; ORR: objective response rate; PoS: probability of success

Similarly, as shown in Appendix H Table 2, when the true ORR is 20%, there is about 17% chance to terminate the 120 mg arm at the first interim futility analysis; about 66% chance to terminate the arm at either the first or second interim futility analysis; PoS at primary analysis is around only 2%. When the true response rate is 35%, the cumulative probabilities of terminating the arm are reduced to 1% and 4% at the first and second interim futility analyses, the probability of success at primary analysis is about 93%.

Appendix I Statistical Guidance on Unacceptable Toxicity and Treatment Related Death

The Bayesian toxicity monitoring approach based on posterior probability will be implemented to each DMC data review up to the second interim futility analysis to continuously monitor the unacceptable toxicity (particularly for Grade ≥4 nonhematologic treatment-related TEAEs) and treatment-related death within each treatment arm separately at various time points.

These toxicity monitoring rules can be translated to toxicity boundaries in terms of the number of patients with Grade ≥4 nonhematologic treatment-related TEAEs and the number of treatment related death among all patients treated for each arm at each safety review. Appendix I Table 1 illustrates the toxicity boundaries with the expected numbers of treated patients for each IDMC safety review based on our most recent enrollment projection. The actual toxicity boundaries will be recalculated based on the observed number of treated patients at each safety review using the same posterior probability stopping rule.

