6.2 Number of Patients

For Part 1, the number of evaluable patients is planned to be 36 to 51.

For Part 2, a total of approximately 25 patients will be enrolled in each expansion cohort. The planned expansion cohorts include 3 modakafusp alfa single-agent cohorts plus at least one combination cohort of modakafusp alfa with dexamethasone using the same dose and schedule of modakafusp alfa used in a single-agent expansion cohort (approximately 100 patients).

For Part 3, approximately 236 patients (118 per dose cohort) will be enrolled.

After global patient enrollment is completed in Part 3, enrollment will continue for the China continuation cohort until about 15% of the total sample size is reached at the selected dose(s) (eg, 18 patients based on 118 patients treated at the selected dose[s]).

Details on the definition of evaluable patients and sample size are given in Section 13.0.

The study is planned to be conducted globally at approximately 100 investigational centers.

6.3 **Duration of Study**

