13.2.2.2 Part 3 Continuous Safety Monitoring Plan and Stopping Rules

In the Part 3 extension cohorts, an IDMC will review accumulating safety, tolerability, and efficacy data. Grade ≥4 nonhematologic treatment-related TEAEs, as well as treatment-related deaths, will be continuously monitored at the following time points using a Bayesian toxicity monitoring approach based on posterior probability (Table 13.b).

Table 13.b Safety Monitoring Time Points Based on Bayesian Stopping Rules

	Time Point
1st DMC Safety review	20 patients have been treated (10 patients in each arm).
2 nd DMC Safety review (first futility analysis)	15 patients in each arm treated for at least 3 cycles or discontinued treatment prematurely.
3 rd DMC Safety review (second futility analysis)	48 patients in each arm treated for at least 3 cycles or discontinued treatment prematurely.

DMC: Data Monitoring Committee.

The stopping rules will be determined based on the posterior probability of the unacceptable toxicity event rate >25%, and the unacceptable treatment-related death rate >5%. If there is at least an 80% probability that the true toxicity event (Grade ≥4 nonhematologic treatment-related TEAEs) rate is greater than 25% given the observed toxicity data, the enrollment will be paused until the IDMC reviews the data to avoid putting more patients at risk.

Similarly, if there is at least an 80% probability that the true treatment-related death rate is greater than 5% given the observed death data, the enrollment will be paused until the IDMC reviews the data. Details of the Bayesian toxicity monitoring plan and the operating characteristics can be found in Appendix I.

If the trial is stopped or paused for unacceptable toxicity or death, the regulatory agencies and investigators will be informed.

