The purpose of the China continuation cohort is to allow continued evaluation of efficacy and any emerging safety signals in Chinese patients enrolled in China. After global patient enrollment is completed in Part 3, enrollment will continue for the China continuation cohort until about 15% of the total sample size is reached at the selected dose(s) (eg, 18 patients based on 118 patients treated at the selected dose[s]).

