Appendix I Table 1 Bayesian Toxicity Monitoring Boundaries for Grade ≥4
Nonhematologic Treatment-Related TEAEs and Treatment RelatedDeaths for Each Treatment Arm

Number of treated patients per arm	Unacceptable toxicity if the number of patients with Grade ≥4 nonhematologic treatment-related TEAEs	Unacceptable toxicity if the number of patients with treatment-related death
10	≥4	≥1
35 a	≥11	≥3
65 a	≥20	≥5

^a The expected numbers of patients treated at IA1 and IA2 based on most recent enrollment projection.

Based on the toxicity boundaries presented in Appendix I Table 1, the corresponding operating characteristics for Grade \geq 4 nonhematologic treatment-related TEAE monitoring for each treatment arm and the cumulative probability of early detection of unacceptable toxicity under different true toxicity rates with the expected number of patient treated at each safety review are displayed in Appendix I Table 2.

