7.13 Interim Analyses and Criteria for Early Termination

Part 2

A futility analysis will be conducted when 10 response-evaluable patients in a phase 2 arm have been followed for at least 3 cycles or have already responded or withdrawn. An arm with the predictive probability <15% (i.e., 3 or fewer responders in 10 patients) will stop enrollment for futility. Overall, avoidance of futility requires 11 or more responders out of the 25 patients to achieve 90% of the overall posterior probability of success (PPOS) at the final analysis. Unless all 25 patients have already been enrolled, another futility analysis with the same decision rule based on PPOS will be conducted when 15 response-evaluable patients in a phase 2 arm have been followed for at least 3 cycles or have already responded or withdrawn. If there are 5 or fewer responders in 15 patients, enrollment will stop for futility. However, the study team reserves the rights to continue the study if the patients still benefit from the study drug.

Part 3

In the Part 3 extension cohorts, an independent data monitoring committee (DMC) will review accumulating safety, tolerability, and efficacy data. The first DMC meeting will occur after approximately 20 patients (approximately 10 patients from each arm) have been enrolled and treated. The second and third DMC meeting will occur at the first and second interim futility analysis when approximately 30 and 96 patients (approximately 15 and 48 patients from each arm) have been enrolled and have completed 3 cycles of treatment or discontinue the treatment prematurely. The subsequent DMC meetings will be approximately every 6 months thereafter.

Futility Stopping Rules

Two interim analyses for futility are planned for the Part 3 extension cohorts when approximately 15 and 48 patients of the planned 118 patients per arm are enrolled and treated for at least 3 cycles or have discontinued treatment prematurely. The futility stopping boundary will be determined based on the predictive probability of success at the primary analysis, using a Bayesian efficacy monitoring approach. The treatment arm will be dropped for futility if the predictive probability of success at the primary analysis is found to be <10% based on the data

CONFIDENTIAL

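### The Part 3 toxicity and death boundaries end at the second futility look, so about 53 of 118 patients per arm would be enrolled with no prespecified pause boundary

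*Protocol*

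**What the plan says.** Protocol 13.2.2.2 pauses enrollment for IDMC review when the posterior probability is at least 80% that the Grade ≥4 nonhematologic related TEAE rate exceeds 25%. It does the same for deaths: "if there is at least an 80% probability that the true treatment-related death rate is greater than 5% given the observed death data". Protocol Table 13.b and SAP Table 4 (Section 7.13) list three time points, the last being the second futility analysis. Protocol Appendix I and SAP Appendix E confirm the end point: the rule "will be implemented to each DMC data review up to the second interim futility analysis".

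The boundary table has rows for 10, 35 and 65 treated per arm. Its footnote calls the last two "The expected numbers of patients treated at IA1 and IA2 based on most recent enrollment projection". The planned size is larger: "For Part 3, approximately 236 patients (118 per dose cohort) will be enrolled". After the second look, SAP 7.13 says: "The subsequent DMC meetings will be approximately every 6 months thereafter". No boundary is attached to those meetings, and the protocol's own table does not list them. At the selected dose, "enrollment will continue for the China continuation cohort until about 15% of the total sample size is reached", so enrollment there may run past 118.

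**The concern.** The monitoring plan is titled continuous, and the sponsor judged a numerical trigger worth having for roughly the first 65 patients per arm. The trigger then lapses while a large share of the arm is still to be enrolled, and while committee meetings that could apply it are already planned. If the true rate of related deaths or severe related toxicity is above the stated limit but the early looks miss it, nothing in the protocol or SAP obliges a pause later.

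The question is not academic here. Protocol 1.3 records that Amendment 10 v2 was an urgent safety measure after a SUSAR, aimed at fatal hemorrhage. That amendment responded with patient-level bleeding rules (Table 8.e). It left the arm-level boundaries as they were.

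**Working it through.** **Inputs.** Limits 25% and 5%, cut-off 80% (Protocol 13.2.2.2). Looks at 10, 35 and 65 treated per arm; boundaries 4/11/20 for toxicity and 1/3/5 for deaths (Appendix I Table 1). 118 per arm (Protocol 6.2). The documents state no prior for this rule.

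**Step 1: reproduce the boundaries.** The boundary at n is the smallest x with P(p > p0 | Beta(a + x, b + n − x)) ≥ 0.80. With a = b = 0.5 all six are recovered. For example, at n = 65, 19 toxicity events give 0.787 and 20 give 0.858; 4 deaths give 0.690 and 5 give 0.843. At n = 10, one death gives 0.801. Beta(1, 1) fails: it gives 19, not 20, for toxicity at 65.

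**Step 2: reproduce the operating characteristics.** Exact binomial recursion over 10, 35 and 65, removing paths that have crossed, gives these cumulative detection probabilities at 65:
- Toxicity at true rates 15/20/25/30/35%: 5.7/16.9/39.1/67.3/88.3%, against the printed 6/17/39/67/88%.
- Deaths at true rates 1/3/5/7/9%: 9.8/30.0/51.9/71.3/85.0%, against the printed 10/30/52/71/85%.

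**Step 3: patients after the last boundary.** 118 − 65 = 53 per arm, or 53/118 = 45%. The look is triggered by 48 patients with 3 cycles or early discontinuation, so the most that could remain is 118 − 48 = 70. Fewer than 53 remain if accrual is faster than projected.

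**Step 4: carry the rule to one later look.** The position of the look is an assumption. 92 is about midway through the remaining 53. A rough projection from the plan's own figures puts a 6-monthly meeting later. The projection has 35 − 15 = 20 and 65 − 48 = 17 further patients per arm treated over about 12 weeks (3 cycles), or 1.7 and 1.4 per week. After 26 weeks that gives 65 + 43 = 108 or 65 + 37 = 102. So looks at 100 and 105 are shown as well. The boundaries (toxicity/deaths) are 27/7 at 92, 29/7 at 100 and 30/8 at 105.

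Cumulative probability of crossing, with Beta(0.5, 0.5):

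| True rate | Current plan (to 65) | + look at 92 | + look at 100 | + look at 105 |
|---|---|---|---|---|
| Death 1% | 10% | 10% | 10% | 10% |
| Death 5% | 52% | 54% | 55% | 54% |
| Death 7% | 71% | 75% | 78% | 75% |
| Death 9% | 85% | 89% | 91% | 90% |
| Grade ≥4, 15% | 6% | 6% | 6% | 6% |
| Grade ≥4, 25% | 39% | 43% | 44% | 45% |
| Grade ≥4, 30% | 67% | 75% | 77% | 79% |

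The death figures do not rise steadily with n because the boundary steps from 7 to 8. Like the plan's own tables, these figures ignore futility stopping.

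**The case against.** The strongest reply is that this is a defensible design choice. Protocol and SAP agree on three time points, so there is no contradiction. The IDMC goes on meeting and may recommend modification or termination (Protocol 3.3.2), and the sponsor may drop an arm for an unfavorable risk-benefit profile on interim data (Protocol 6.1). At a scheduled meeting the committee is already reviewing, so a crossed boundary adds only a prespecified prompt. Criteria for later reviews may also stand in the IDMC charter, which is not among the documents. All of this stands. It limits the point to a missing trigger in the protocol and SAP, with a modest gain.

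A reader might infer more, and the documents do not support it:
- **That safety monitoring ends at the second look.** It does not; only the numerical rule ends.
- **That the later patients are the most exposed.** They are 45% of the arm and enter last, so at any given review they have the shortest exposure.
- **That a look at 118 treated would add further protection.** The rule's only action is to pause enrollment. At 118 the main cohort is full, and only the China continuation cohort could be paused. Gains from such a look are therefore left out.

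Two provisions might seem to close the gap. Appendix I says: "The actual toxicity boundaries will be recalculated based on the observed number of treated patients at each safety review". That adjusts the boundary at reviews the rule covers and does not extend it to later ones. Protocol 8.3 has trial-level thresholds (6% related fatal events, 10% related Grade 4 events in a nonhematologic SOC, 40% DLT-type events). They sit under the Part 1 escalation rules, with fatal-event counts set for 30 patients at one dose and schedule. The documents do not say whether they govern Part 3.

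**Conclusion.** The point holds as an inexpensive improvement, not as an error. In an arm that passes both futility looks, about 53 of 118 patients would be enrolled after the last prespecified boundary.

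One added look while enrollment is open raises detection by about 4 to 6 percentage points at a 7% or 9% death rate, and by about 8 to 12 points at a 30% Grade ≥4 rate. A pause could spare at most 118 − 92 = 26 patients per arm at a look at 92, and 18 to 13 at a look at 100 to 105.

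The result rests on three assumptions: a Beta(0.5, 0.5) prior, inferred because it reproduces every printed figure; the projected 65 treated at the second look; and the placing of the added look.

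**What to change.** In Protocol Appendix I and SAP Appendix E, remove the limit that ends the rule at the second futility look. Apply the same posterior rule, with the same 25%, 5% and 80% values and recalculated to the observed treated number, at every later scheduled DMC review held while the arm is enrolling. Include the China continuation cohort. State the prior. Add an illustrative row, for example ≥27 Grade ≥4 events or ≥7 deaths at 92 treated, with its operating characteristics. List the later reviews in Protocol Table 13.b and SAP Table 4, and say whether the Section 8.3 thresholds apply to Part 3 so that the two sets can be reconciled.

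The cost is wording and table rows; no added patients or meetings are needed. The statistical price is a higher chance of a pause at the limits themselves: from 52% to 54–55% at a 5% death rate, and from 39% to 43–45% at a 25% Grade ≥4 rate. There is no material change at a 1% death rate or a 15% toxicity rate.

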Appendix I Table 2 Operating Characteristics for Monitoring Grade ≥4

Nonhematologic Treatment-Related TEAEs Within Each Treatment Arm

True	Cumulative probability of early detection with number of treated patients		
Toxicity rate	10 patients	35 patients	65 patients
15%	5%	6%	6%
20%	12%	16%	17%
25%	22%	35%	39%
30%	35%	58%	67%
35%	49%	78%	88%

TEAE: treatment-emergent adverse event.

As shown in Appendix I Table 2, when the true toxicity rate is as low as 15%, there are low cumulative probabilities of 5% to 6% for early calls of unacceptable toxicity at each safety review; when the true toxicity rate is as high as 35%, there are about 49% to 88% cumulative probabilities of early call for unacceptable toxicity at each safety review. When the true DLT rate is 25% (the maximum toxicity allowed), there is about 39% cumulative probability to have an early call for unacceptable toxicity.

Similar operating characteristics table was created for monitoring of treatment-related death for each treatment arm, shown in Appendix I Table 3.

Appendix I Table 3 Operating Characteristics for Monitoring Treatment-Related Death Within Each Treatment Arm

True	Cumulative probability of early detection with number of treated patients			
Toxicity rate	10 patients	35 patients	65 patients	
1%	10%	10%	10%	
3%	26%	29%	30%	
5%	40%	48%	52%	
7%	52%	64%	71%	
9%	61%	76%	85%	

As shown in Appendix I Table 3, when the true treatment-related death rate is as low as 1%, there is about 10% cumulative probability of early call of unacceptable toxicity at each safety review; when the true treatment related death rate is as high as 9%, there are about 61% to 85% cumulative probabilities of early toxicity call at each safety review. When the true treatment-related death rate is 5% (the maximum toxicity allowed), there is about 52% cumulative probability to alarm the unacceptable toxicity early.

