Appendix E Statistical Guidance on Unacceptable Toxicity and Treatment Related Death

The Bayesian toxicity monitoring approach based on posterior probability will be implemented to each DMC data review up to the second interim futility analysis to continuously monitor the unacceptable toxicity (particularly for Grade ≥ 4 nonhematologic treatment-related TEAEs) and treatment-related death within each treatment arm separately at various time points.

These toxicity monitoring rules can be translated to toxicity boundaries in terms of the number of patients with Grade ≥ 4 nonhematologic treatment-related TEAEs and the number of treatment related death among all patients treated for each arm at each safety review. Appendix I Table 1 illustrates the toxicity boundaries with the expected numbers of treated patients for each IDMC safety review based on our most recent enrollment projection. The actual toxicity boundaries will be recalculated based on the observed number of treated patients at each safety review using the same posterior probability stopping rule.

Appendix E Table 1 Bayesian Toxicity Monitoring Boundaries for Grade ≥ 4 Nonhematologic Treatment-Related TEAEs and Treatment Related- Deaths for Each Treatment Arm

Number of treated patients per arm	Unacceptable toxicity if the number of patients with Grade ≥ 4 nonhematologic treatment-related TEAEs	Unacceptable toxicity if the number of patients with treatment-related death
10	≥ 4	≥ 1
35 ^a	≥ 11	≥ 3
65 ^a	≥ 20	≥ 5

^a The expected numbers of patients treated at IA1 and IA2 based on most recent enrollment projection.

Based on the toxicity boundaries presented in Appendix E Table 1, the corresponding operating characteristics for Grade ≥ 4 nonhematologic treatment-related TEAE monitoring for each treatment arm and the cumulative probability of early detection of unacceptable toxicity under different true toxicity rates with the expected number of patient treated at each safety review are displayed in Appendix E Table 2.

Appendix E Table 2 Operating Characteristics for Monitoring Grade \geq 4 Nonhematologic Treatment-Related TEAEs within Each Treatment Arm

True Toxicity rate	Cumulative probability of early detection with number of treated patients		
	10 patients	35 patients	65 patients
15%	5%	6%	6%
20%	12%	16%	17%
25%	22%	35%	39%
30%	35%	58%	67%
35%	49%	78%	88%

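### The Part 3 toxicity and death boundaries count every treated patient as fully observed, so the alarm probabilities in Appendix I are upper limits unless events occur almost at once

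*Protocol*

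**What the plan says.** Protocol Section 13.2.2.2 and SAP Section 7.13 pause enrollment for IDMC review if the posterior probability is at least 80% that the Grade ≥4 nonhematologic treatment-related TEAE rate exceeds 25%, or that the treatment-related death rate exceeds 5%. Protocol Appendix I turns this into counts per arm, for deaths "the number of treatment related death among all patients treated for each arm at each safety review". SAP Appendix E repeats the rule and adds: "The actual toxicity boundaries will be recalculated based on the observed number of treated patients at each safety review".

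The triggers in Protocol Table 13.b are:

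- Review 1: "20 patients have been treated (10 patients in each arm"), with no follow-up requirement.
- Review 2: "15 patients in each arm treated for at least 3 cycles or discontinued treatment prematurely".
- Review 3: the same condition with 48 patients per arm.

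Appendix I Table 1 gives boundaries at 10, 35 and 65 treated patients per arm: 4/11/20 for toxicity and 1/3/5 for deaths. Its footnote explains 35 and 65: "The expected numbers of patients treated at IA1 and IA2 based on most recent enrollment projection". Tables 2 and 3 then state detection by number treated. At 35% toxicity, for example, "there are about 49% to 88% cumulative probabilities of early call for unacceptable toxicity at each safety review".

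Neither document gives an observation window for the monitored rates, the prior used for them, or any data on event timing. In Part 3, treatment may run to progression (Protocol 9.4), and the SAP counts TEAEs to 30 days after the last dose (7.12.1).

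**The concern.** A patient dosed shortly before a review adds one to the denominator but has had little time to add to the numerator. The futility rule, applied at the same meetings as reviews 2 and 3, avoids this by counting patients followed for 3 months (Protocol Table 13.a). The safety rule does not.

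The error runs in one direction only, toward no alarm. An IDMC member reading Tables 2 and 3 would take them as the chance that a dose above the 25% or 5% limit is flagged, and that chance may be lower than printed. The death rule matters in practice: Amendment 10 v2 was prompted by a SUSAR and aims to reduce the risk of fatal hemorrhage.

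**Working it through.** **1. Reproduce the boundaries.** Find the smallest x with P(rate > limit | Beta(a + x, b + n − x)) ≥ 0.80. The prior is not stated. Beta(0.5, 0.5) returns all six boundaries:

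| n | Toxicity (limit 25%) | Death (limit 5%) |
|---|---|---|
| 10 | x=3: 0.662; x=4: 0.862 | x=0: 0.305; x=1: 0.801 |
| 35 | x=10: 0.696; x=11: 0.812 | x=2: 0.621; x=3: 0.839 |
| 65 | x=19: 0.787; x=20: 0.858 | x=4: 0.690; x=5: 0.843 |

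**2. Reproduce Tables 2 and 3.** Treat each treated patient as one completed Bernoulli trial and run the exact sequential binomial over 10, 35 and 65. At 35% toxicity this gives 48.6/78.5/88.3% (stated 49/78/88%). At a 9% death rate it gives 61.1/76.4/85.0% (stated 61/76/85%); the first look is 1 − 0.91^10 = 0.611. All 30 entries agree within 1 point. The tables are therefore correct on their own basis, which is full observation of everyone treated.

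**3. Compare with the triggers.** At review 2, 35 − 15 = 20 of 35 patients (57%) lie outside the trigger. At review 3, 65 − 48 = 17 of 65 (26%) do. Review 1 sets no follow-up at all.

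**4. Follow-up implied by the projection (assumption: even accrual, 84 days for 3 cycles).** Twenty patients enter in the 84 days before review 2, so spacing is 84/20 = 4.2 days up to patient 35. Seventeen enter in the 84 days before review 3, so spacing is then 84/17 = 4.94 days. For a 28-day window, the share of risk time observed is:

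- Review 1, cut at the tenth first dose: follow-up is 0, 4.2, …, 25.2 days for seven patients (sum 88.2) and at least 28 for three. (88.2 + 3×28)/280 = 61%.
- Review 2: (88.2 + 28×28)/980 = 89%.
- Review 3: six patients have under 28 days (sum 15×4.94 = 74.1). (74.1 + 59×28)/1820 = 95%.

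**5. Effect on the alarm (assumption: onset uniform over the stated period).** Events count only if they precede the review. Entries are cumulative alarm in %, by simulation, at reviews 1/2/3:

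| Case | Toxicity 35% | Death 9% |
|---|---|---|
| Stated | 49/78/88 | 61/76/85 |
| 7-day onset, review 1 cut at tenth first dose | 35/72/85 | 56/73/83 |
| 7-day onset, cut one cycle later | 49/75/86 | 61/75/84 |
| 28-day onset, cut at tenth first dose | 14/57/77 | 44/66/79 |
| 28-day onset, cut one cycle later | 49/67/82 | 61/72/82 |

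Hand check of one cell: for death at review 1 with 28-day onset and the early cut, 1 − (1 − 0.09×0.615)^10 ≈ 43%, against 44% simulated.

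**The case against.** The strongest reply is that the shortfall is conditional. The documents give no event timing, and early onset is plausible: Appendix I at one point calls the 25% limit a DLT rate, and Part 1 DLTs are events before Cycle 2 Day 1 (Protocol 8.2). Infusion-related reactions occur during or shortly after dosing. SAP 7.13 places the first meeting after about 20 patients have been treated, so the data cut may come later than the tenth first dose. With 7-day onset and a cut one cycle later, the tables are missed by at most about 4 points and review 1 not at all. This stands, and it limits the size. It does not remove the gap, because neither condition is written down.

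A reader might infer a much larger loss. With onset spread over three cycles and the early cut, 35% toxicity gives only about 0.4/21/53%. The documents do not support that onset pattern, so the figure should not be used as an estimate. They do not exclude later events either: Section 8.2 foresees DLT-like events after Cycle 1.

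A reader might also infer that this is the only formal toxicity rule bearing on Part 3, or that an arm below the boundary is cleared. Neither follows. Section 8.3, under a Part 1 heading, states thresholds for stopping the trial on related fatal events, related Grade 4 events and DLT-type events. The IDMC reviews all accumulating safety data and can recommend modification or termination whether or not a boundary is crossed.

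**Conclusion.** The concern holds in conditional form. The boundaries treat all treated patients as fully observed, the triggers guarantee that many are not, and the 25% and 5% rates have no time base. The alarm probabilities in Appendix I Tables 2 and 3 (SAP Appendix E Tables 2 and 3) are therefore upper limits unless events are almost immediate.

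With one-cycle onset, the shortfall at 35% toxicity is 35/21/11 points with the early cut (49−14, 78−57, 88−77) or 0/11/6 with the later one. At a 9% death rate it is 17/10/6 or 0/4/3 points. These figures rest on even accrual matching the projection, all 15 and 48 trigger patients having 84 days, uniform onset, and the inferred Beta(0.5, 0.5) prior. The direction is firm; the size is not known from the documents. A claim that the rates are understated at every review by a known amount would go too far.

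**What to change.** Amend Protocol Appendix I and SAP Appendix E. Keep the 25% and 5% limits and the 80% threshold.

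1. Define both monitored rates over a fixed window, for example one 28-day cycle from first dose, and state the prior.
2. Keep review 1 at its trigger with the current boundaries. Re-apply them to the first 10 patients per arm once each has completed the window or had an event. This is the step that helps the death rule: with 28-day onset it moves the 9% row from 44/66/79% to about 61/72/82%.
3. At reviews 2 and 3, use a follow-up-weighted denominator for toxicity: a patient with the event counts 1, any other counts min(1, days since first dose / window). The death boundaries stay at 3 and 5 under this weighting, so it does not improve the death alarm.
4. Restate Tables 2 and 3 for the follow-up expected at each review, with a sensitivity range for event timing.

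With 28-day onset, steps 2 and 3 together give about 49/74/87% at 35% toxicity and 5–6% at an acceptable 15% (stated 5/6/6%). Weighting should not be applied at review 1 in place of the re-check: with 7-day onset and the early cut, that raises the alarm at 15% toxicity to about 13%.

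The cost is wording in the protocol, SAP and IDMC charter, one rerun of the operating characteristics, one extra look at the first 10 patients per arm, possibly a few more pauses for IDMC review, and less favorable stated detection figures.
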